6.2.7.5. Time-to-Deterioration Analysis

A 3-point change in FBISI-DRS-P has been established as clinically meaningful. Time to deterioration (TTD) is defined as the time from the date of randomization to the first time the patient's score shows a 3 point or greater decrease from baseline in FBISI-DRS-P for 2 consecutive assessments.

Patients will be censored at the last time when they completed the assessment if they have not deteriorated.

TTD will be analyzed by a log-rank test stratified by randomization stratification factors. The time to deterioration in each treatment arm will be summarized using the Kaplan-Meier method and displayed graphically where appropriate. Confidence intervals (CIs) for the 25th, 50th and 75th percentiles will be reported. The Cox proportional hazards model will be fitted to compute the treatment hazard ratios and the corresponding 95% CI.

Sensitivity analyses based on a 2- and 4-point decrease from baseline in FBISI-DRS-P will also be conducted to assess the robustness of the TTD analyses. Cumulative distribution plots of FBISI-DRS-P will also be presented on Day 1 of Cycles 2, 4 and 6.

6.2.7.6. Random Coefficient Models

Random coefficient models will be carried out for the NCCN-FACT FBISI-18 and all subscales (DRS-P, DRS-E, TSE, and F/WB), EQ-5D-5L, and EQ-VAS using PROC MIXED. Outcomes are PRO post-baseline scores and the predictors are the corresponding baseline PRO score, treatment, time (treated as a continuous variable), and treatment-by-time interaction. Intercept and time are considered as random effects particular to each patient. All available data for each patient should be used in the analyses. All parameter estimates should be obtained using restricted maximum likelihood. The unstructured covariance structure should be used to define covariance between random effects (using option “Type=UN” as a part of the RANDOM statement in PROC MIXED). For the degrees-of-freedom calculations the Kenward and Roger algorithm should be used (using option “ddfm = kr” as a part of the MODEL statement in PROC MIXED).

6.3. Other Endpoints

Not applicable.

6.4. Subset Analyses

Subset analyses will be performed for patients with PD-L1-positive tumors and for patients irrespective of PD-L1 expression.

Subset analyses will be performed for OS, and for PFS, OR and DR per BICR assessment based on the FAS for the subgroups defined below.

The following subgroups will be defined and used for analyses:

- Randomization stratification factors
 - Best response to first-line chemotherapy (CR or PR vs. SD)
 - Metastatic disease site (visceral vs. non-visceral) at the time of initiating first-line chemotherapy.
- Age
 - Age < 65 years (Reference)
 - Age ≥ 65 years
- Gender
 - Male (Reference)
 - Female
- Race
 - White (Reference)
 - Asian

- Black or African American
- Other
- Ethnicity
 - Hispanic or Latino
 - Not Hispanic or Latino (Reference)
- Pooled Geographical Region
 - North America
 - Europe (Reference)
 - Asia
 - Rest of the World (Australasia, Latin America, Africa and/or Middle East will be included as additional subgroups if including > 10% of the overall randomized population)
- PD-L1 status at baseline
 - Positive (Reference)
 - Negative
- First-line chemotherapy regimen
 - Gemcitabine+cisplatin (Reference)
 - Gemcitabine+carboplatin
- ECOG Performance Status
 - 0 (Reference)
 - ≥ 1
- Creatinine Clearance at baseline
 - ≥ 60 mL/min (Reference)
 - < 60 mL/min
- Liver lesions at baseline
 - Yes
 - No
- Lung lesions at baseline
 - Yes

– No

Subset analyses for OS, PFS and DR will use the primary censoring rules described in Sections 6.1.1.1, 6.2.2.1 and 6.2.2.5. All the subgroup analyses are exploratory. Treatment arms will be compared for OS and PFS using a 2-sided unstratified log-rank test for each subgroup level and the unstratified HR and its corresponding 95% CI will be computed per subgroup level.

All the subgroup analyses will be exploratory; no adjustment for multiplicity will be performed. In the case of a low number of patients within a category (<5% of the randomized population), the categories will be pooled, or in cases where no meaningful pooling can be performed, the category may not be summarized.

To assess the heterogeneity of treatment effects for OS and PFS across the subgroup levels, two Cox regression models will be fitted with OS or PFS, respectively, as the dependent variable and subgroup, treatment, and with and without the treatment-by-subgroup interaction as explanatory variables.

- Model 1: factors + treatment + subgroup
- Model 2: factors + treatment + subgroup + treatment × subgroup-variable

A p-value for the interaction test (Wald's test) will be provided together with the HR and corresponding 95% CI for the interaction model parameter.

The HR for OS and PFS and corresponding 95% CIs for all subgroups will also be presented in a forest plot.

The ORR odds ratio for each subgroup and corresponding 95% CIs will also be presented in a forest plot.

6.5. Baseline and Other Summaries and Analyses

6.5.1. Baseline summaries

The following analyses will be performed for patients with PD-L1-positive tumors and for patients irrespective of PD-L1 expression, based on the FAS overall and separately by treatment arm.

6.5.1.1. Demographic characteristics

Demographic characteristics and physical measurements will be summarized by treatment arm using the following information from the 'Screening/Baseline Visit' eCRF pages.

- Demographic characteristics
 - Gender: Male, Female
 - Race: White, Black or African American, Asian, American Indian or Alaska Native, Native Hawaiian or Other Pacific Islander, Other, Unknown

- Ethnic origin:
 - Hispanic or Latino
 - Not Hispanic or Latino
- Age (years): summary statistics
- Age categories:
 - < 65 years, ≥ 65 years
 - < 65, 65-<75, 75-<85, ≥ 85 years
- Pooled Geographical Region (as applicable):
 - North America
 - Europe
 - Asia
 - Rest of the World (Australasia, Latin America, Africa and/or Middle East will be included as additional pooled geographical regions if including > 10% of the overall randomized population)
- Geographic Region (as applicable):
 - North America
 - Latin America
 - Western Europe
 - Eastern Europe
 - Middle East
 - Australasia
 - Asia
 - Africa
- Eastern Cooperative Oncology Group (ECOG) Performance Status: 0, 1, 2, 3, and 4
- Physical measurements
 - Height (cm)
 - Weight (kg)
 - Body Mass Index (BMI) (kg/m²)

Center codes will be used for the determination of the patient's geographic region.

The listing of demographics and baseline characteristics will include the following information: patient identifier, treatment arm, age, sex, race, ethnicity, height (cm), weight (kg), BMI (kg/m²), and ECOG performance status.

6.5.1.2. Medical history

Medical history will be coded using the most current available version of Medical Dictionary for Regulatory Activities (MedDRA) and will be summarized from the ‘Medical History’ eCRF page. Medical history will be summarized as the numbers and percentages of patients by MedDRA preferred term (PT) as event category and MedDRA primary system organ class (SOC) as summary category. Each patient will be counted only once within each PT or SOC.

Medical history will be displayed in terms of frequency tables: ordered by primary SOC and PT in alphabetical order.

6.5.1.3. Disease characteristics

Information on disease characteristics collected on ‘Primary Diagnosis’, ‘Substance Abuse’ and RECIST eCRF pages will be summarized overall and by treatment arm. Summary statistics will be presented for the following.

From the ‘Primary Diagnosis’ eCRF page:

- Site of primary tumor
- Primary diagnosis (summarize all categories collected in the ‘Primary Diagnosis’ eCRF page)
- Time since initial diagnosis to date of randomization (months), defined as (date of randomization – date of initial diagnosis)/30.4375

Separately from the RECIST eCRF page based on Investigator assessment and based on BICR assessment:

- Measurable disease (lesions) at baseline (Yes, No, No disease)
- Involved tumor sites at baseline

From the ‘Substance Use’ eCRF page:

- Smoking history (Never smoker, Current smoker, Former smoker)

Listing of disease history will be provided with all relevant data (as collected on the ‘Primary Diagnosis’ and ‘Substance Use’ eCRF pages) and derived variables as above.

6.5.1.4. Prior anti-cancer therapies

The prior anti-cancer therapies are collected under the ‘Prior Cancer Therapy’, ‘Prior Radiation Therapy’ and ‘Prior Surgery’ eCRF pages.

The number and percentage of patients in each of the following anti-cancer therapy categories will be tabulated:

- Patients with at least one type of prior anti-cancer therapy
- Patients with at least one prior anti-cancer drug therapy
- Patients with at least one prior anti-cancer radiotherapy
- Patients with at least one prior anti-cancer surgery

Prior anti-cancer drug therapy will be summarized as follows based on the number and percentage of patients with the following:

- At least one prior anti-cancer drug therapy
- Number of prior anti-cancer drug therapy regimens: missing, 1, 2, 3, ≥ 4
- Intent of Drug Therapy: Neo-Adjuvant, Adjuvant, Advanced-Metastatic, Locoregional Disease-Recurrence
- Best response: CR, PR, SD, PD, Unknown, Not applicable. Best response is derived from the last treatment regimen.

The prior anti-cancer drugs will also be summarized based on the number and percentage of patients by the drug class and preferred term. A patient will be counted only once within a given drug class and within a given drug name, even if he/she received the same medication at different times. The summary will be sorted on decreasing frequency of drug class and decreasing frequency of drug name in a given drug class. In case of equal frequency regarding drug class (respectively drug name), alphabetical order will be used.

Prior anti-cancer therapies will be included in the listings that follow with a flag to identify prior therapies. These will include the patient identification number, and all the relevant collected data-fields on the corresponding eCRF pages.

- Listing of anti-cancer drug therapies
- Listing of anti-cancer radiotherapy
- Listing of anti-cancer surgeries

6.5.1.5. Exposure to first-line anti-cancer chemotherapy regimen

Exposure to first-line anti-cancer agents will be summarized separately for gemcitabine, cisplatin and carboplatin.

The duration of treatment (in weeks) for each agent is defined as:

$$\text{Treatment duration (weeks)} = (\text{last dose date of gemcitabine or cisplatin or carboplatin} - \text{first dose date of gemcitabine or cisplatin or carboplatin} + 21) / 7$$

The cumulative dose of each agent is the sum of the actual dose levels that the patient received.

The summary of treatment exposure for first-line chemotherapy regimen will include the following information:

- Total number of infusions received for each agent
- Duration of treatment
- Cumulative dose (mg/m² or AUC, as appropriate) for each agent

6.5.2. Study Conduct and Patient Disposition

The following analyses will be performed based on the FAS overall and separately by treatment arm.

6.5.2.1. Patient disposition

The percentages below will be calculated based on the number of patients in the FAS.

- Total number of patients screened overall;
- Number of patients who discontinued from the study prior to randomization overall and by the main reason for discontinuation;
- Number and percentage of randomized patients in each of the analysis sets defined in [Section 4](#);
- Number and percentage of randomized patients with study drug ongoing;
- Number and percentage of randomized patients who discontinued study drug overall and by the main reason for discontinuation of study drug;
- Number and percentage of patients who entered follow-up;
- Number and percentage of patients who discontinued follow-up overall and by the main reason for discontinuation;
- Number and percentage of patients who entered long-term follow-up;
- Number and percentage of patients who discontinued long-term follow-up overall and by the main reason for discontinuation.

The results of the randomization algorithm (according to IRT) will be summarized as follows:

- Number and percentage of randomized patients overall, by region (Europe, EEA (required by EudraCT), North America, Latin America, Middle East, Asia, Australasia, Africa), by country within region;
- Number and percentage of randomized patients by center;

- Number and percentage of randomized patients by randomization strata (IRT);
- Cross tabulation: patients randomized (avelumab + BSC/BSC/none) vs. patients treated (avelumab + BSC/BSC/none).

6.5.2.2. Protocol deviations

All protocol violations that impact the safety of the patients and/or the conduct of the study and/or its evaluation will be reported. These include:

- Patients who are dosed on the study despite not satisfying the inclusion criteria
- Patients who develop withdrawal criteria whilst on the study but are not withdrawn
- Patients who receive the wrong treatment or an incorrect dose
- Patients who receive an excluded concomitant medication
- Deviations from GCP.

The identification of these and other CSR-reportable deviations will be based on the inclusion/exclusion criteria or other criteria presented in the protocol.

6.5.3. Study Treatment Compliance and Exposure

The following analyses will be based on the safety analysis set by treatment arm.

All dosing calculations and summaries will be based on 'Parenteral – Drug avelumab' eCRFs pages. A listing of study drug administration will be created with the information collected on the 'Parenteral – Drug avelumab' eCRF pages.

For Arm B, the duration of BSC treatment will be summarized based on the time from C1D1 through date of discontinuation of BSC as collected in the Disposition eCRF page.

The derivations below are provided for the following:

- Avelumab administered as a 1-hour IV infusion at a dose of 10 mg/kg once every 2 weeks in 4-week cycles.

Analysis of exposure will be based on the calculated actual dose levels:

- Avelumab - total dose / weight

6.5.3.1. Exposure to avelumab

The dose level for avelumab is calculated as actual dose administered/weight (mg/kg). The last available weight of the patient on or prior to the day of dosing will be used.

For Cycle X, actual cycle start date for each patient is

- the start date of dosing in the Cycle X day 1 visit eCRF exposure page, if the patient received avelumab on that visit (ie, avelumab with dose>0 at that visit)

- the first day of assessments in the Cycle X day 1 visit, if the patient did not receive avelumab on that visit (ie, dose=0 for avelumab at that visit). Use start date in the exposure page if available; if start date is not available then use date of collection of vital signs on Cycle X day 1 visit.

Actual cycle end date for each patient is,

- for all cycles X except the last cycle, actual cycle end date = actual cycle (X+1) start date – 1 day;
- for the last cycle, actual cycle end date = actual cycle start date + 28 – 1 day

Cycle duration (weeks) = (actual cycle end date – actual cycle start date + 1)/7

Intended duration of treatment with avelumab (weeks) =

(end date – date of first dose of avelumab + 1)/7,

where end date = start date of last cycle with non-zero dose of avelumab + 28 – 1

Duration of exposure to avelumab (weeks) =

(last dose date of avelumab – first dose date of avelumab + 14)/7

Cumulative dose is the sum of the actual doses of avelumab received.

Actual Dose Intensity (DI)

- Overall actual DI (mg/kg/4-week cycle) = [overall cumulative dose (mg/kg)] / [intended duration of treatment with avelumab (weeks)/4].

Relative Dose Intensity (RDI)

- Intended DI (mg/kg/4-week cycle) = [intended cumulative dose per cycle] / [intended number of 4-weeks in a cycle] = [20 (mg/kg)] / [1 (4-week cycle)] = 20 (mg/kg/4-week cycle)
- Overall RDI (%) = $100 \times [\text{overall actual DI}] / [\text{intended DI}]$
= $100 \times [\text{overall actual DI}] / [20 \text{ (mg/kg/4-week cycle)}]$

6.5.3.2. Dose reductions

Applicable to avelumab.

Dose reduction is defined as actual non-zero dose < 90% of the planned dose.

The number and percentage of patients with at least one dose reduction as well as a breakdown of the number of dose reductions (1, 2, 3, ≥4) will be summarized for Arm A.

6.5.3.3. Dose delays

Applicable to avelumab.

Dose Delay is the difference between the actual time between two consecutive non-zero doses and the planned time between the same two consecutive non-zero doses.

In Cycle 1,

$$\text{Dose Delay (days)} = \text{day of first dose of avelumab} - 1.$$

After the first dose of Cycle 1

$$\text{Dose Delay (days)} = \text{Date of dose } x \text{ of avelumab} - \text{Date of dose } (x-1) \text{ of avelumab} - 14.$$

Dose delays will be grouped into the following categories:

- No delay
- 1-3 days delay
- 4-6 days delay
- 7 or more days delay

For example, for avelumab, administered on a 2-week schedule, if one patient receives avelumab on Day 1, then the next avelumab administration date will be on Day 15; however, if the patient receives avelumab at Day 16, 17 or 18, this is considered as 1-3 days delay.

No delay and 1-3 days delay will also be summarized together.

Number and percentage of patients with delayed study drug administration and maximum length of delay, ie the worst case of delay if patients have multiple dose delays will be summarized for Arm A.

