5.4.3. Recommended Dose Modifications

Every effort should be made to administer study treatment on the planned dose and schedule.

For avelumab, no dose modifications are permitted in this study, but next infusion may be omitted based on persisting toxicity. Recommended toxicity management guidelines with regard to avelumab infusion omissions are shown in Table 3.

Table 3. Avelumab Infusion Omissions for Avelumab Product-Related Toxicity

| Toxicity | NCI CTCAE Severity Grade | Avelumab |
|---|--------------------------|---|
| | | Treatment Modification |
| Infusion-related Reaction / Hypersensitivity | Grade 1-4 | 
 See Section 5.4.3.2 and Table 4. |
| Tumor lysis syndrome | Grade 1-4 | 
 See Section 5.4.3.3 and Figure 2. |
| Immune-related AE (irAE) | Grade 1-4 | 
 See Section 5.4.3.4 and Table 5. |
| Drug-related adverse reactions (excluding infusion-related reaction / hypersensitivity and immune-related AE) | Grade 1 | 
 Continue as per schedule. |
| | Grade 2 | 
 Continue as per schedule. |
| | Grade 3 | 
 Withhold until recovery to Grade \leq1 or baseline. Permanently discontinue if toxicities do not resolve to Grade \leq1 or baseline within 12 weeks of last administration or if the same Grade 3 toxicity recurs. 
Exceptions are:
 
 Laboratory values out of normal range that do not have any clinical correlate. |
| | Grade 4 | 
 Permanently discontinue. 
Exceptions are:
 
 Laboratory values out of normal range that do not have any clinical correlate. |

Avelumab infusion-related reactions (including hypersensitivity) and irAEs should be handled according to guidelines in [Section 5.4.3.2](#) Management of Avelumab Infusion-Related Reactions and [Section 5.4.3.4](#) Management of Avelumab Immune-Related Adverse Events.

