5.2.4. Definition of study day

Start day of study treatment is the day of the first dose of study treatment in Arm A, and the day of Cycle 1 Day 1 in Arm B.

The study day for assessments occurring on or after the start of study treatment (eg, adverse event onset, tumor measurement) will be calculated as:

Study day = Date of the assessment/event - start of study treatment + 1.

The study day for assessments occurring prior to the first dose of study treatment (eg, baseline characteristics, medical history) will be negative and calculated as:

Study day = Date of the assessment/event - start of study treatment.

The study day will be displayed in all relevant data listings.

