6.6.1.3. Adverse events leading to interruption of study treatment

Applicable to Arm A only.

The eCRF does not allow for a clear separation between interruption of an infusion and delays of administration for a parenteral drug as both are recorded using the same term on the eCRF (“Drug interrupted”). IRRs will be excluded in the analysis of AEs leading to Drug Interruption in case they only led to an interruption of the infusion (ie, did not lead to a dose reduction or a dose delay).

As such, AEs leading to interruption will be defined as AEs identified in the AE eCRF page with an action taken with study treatment of ‘drug interrupted’ excluding

- IRRs that occurred on the day of infusion with $\geq 90\%$ of the planned dose given (ie IRRs that did not lead to a dose reduction) and subsequent administration of study drug had no delay (as defined in Section 6.5.3.3). These IRRs will be considered as IRRs leading to interruption of infusion.
- IRRs occurring on the day after infusion and subsequent dose administration had no delay (as defined in Section 6.5.3.3).

The frequency (number and percentage) of patients with each of the following will be presented for TEAEs leading to interruption of avelumab for Arm A:

- TEAEs leading to interruption of avelumab by SOC and PT

The listing of all AEs leading to interruption of study treatment will also be provided with the relevant information.

In addition, the frequency (number and percentage) of patients with each of the following will be presented for TEAEs leading to interruption of avelumab for Arm A:

- TEAEs leading to both interruption and dose reduction of avelumab by SOC and PT

This summary will take into account PTs with both actions as defined in Section 6.6.1, even though the actions may be captured for different PT records (ie, different onset for the PT with action “drug interrupted” and the PT with action “dose reduced”).

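### SAP 6.5.3.3 defines dose delay in words that disagree with its own formula when an infusion is omitted, and the strict no-delay test in 6.6.1.3 counts infusion reactions as treatment interruptions when the next dose is only 1 to 3 days late

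*SAP*

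**What the plan says.** **Dose delay (SAP 6.5.3.3).** In words, delay is the actual time between two consecutive non-zero doses minus the "planned time between the same two consecutive non-zero doses". The formula then given is the date of dose x minus the date of dose x-1 minus 14. It does not say whether x counts only non-zero doses. For Cycle 1 the delay is the "day of first dose of avelumab" minus 1. Results are grouped as no delay, 1-3 days, 4-6 days, and 7 or more days; the first two groups are also reported pooled. A worked example starts from a dose on Day 1: "if the patient receives avelumab at Day 16, 17 or 18, this is considered as 1-3 days delay".

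**Day 1 (SAP 5.2.4).** "Start day of study treatment is the day of the first dose of study treatment in Arm A". SAP 3.4.1 takes the first dose as the earliest non-zero dosing.

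**Omission (Protocol 5.4.3).** For avelumab, "no dose modifications are permitted in this study, but next infusion may be omitted based on persisting toxicity". Protocol 5.4 says the same and rules out dose reduction for toxicity.

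**Use in the adverse-event tables (SAP 6.6.1.3).** The section starts from events recorded with the action 'drug interrupted' and aims to remove IRRs that only paused the infusion. An IRR on the day of infusion is removed if at least 90% of the planned dose was given and "subsequent administration of study drug had no delay (as defined in Section 6.5.3.3"). An IRR on the day after infusion is removed if the next dose had no delay.

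**The concern.** Omission is an action the protocol explicitly provides for, yet the SAP does not say how an omitted infusion enters the delay calculation. Two programmers could each follow SAP 6.5.3.3 faithfully and place the same patient in opposite categories of the maximum-delay table.

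The post-first-dose rule is then reused in 6.6.1.3 to decide which IRRs count as leading to interruption of avelumab. That count appears in the overall adverse-event summary (SAP 6.6.1.1) and by system organ class and preferred term (SAP 6.6.1.3). At stake is whether these tolerability tables mean what their titles say.

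The Cycle 1 delay is a separate, smaller matter: a quantity that is zero by construction carries no information about late starts.

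**Working it through.** **Inputs.** Definition, formulas, categories and example: SAP 6.5.3.3. Day 1 and study-day formula: SAP 5.2.4 and 3.4.1. Dosing every 2 weeks on Days 1 and 15 of a 4-week cycle: Protocol 5.4. Visit window of ±3 days: Protocol Schedule of Activities. IRR exclusion: SAP 6.6.1.3.

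**Step 1. Reproduce the SAP example.** First dose on Day 1, formula = next day - 1 - 14.
- Day 15: 15 - 1 - 14 = 0, no delay.
- Days 16, 17, 18: 1, 2, 3, category 1-3 days, as the SAP states.

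With nothing omitted, the words and the formula agree.

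**Step 2. Omit infusions, then resume on schedule.** Three readings are possible.

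| Doses given | Words: actual - planned | Formula, x = non-zero doses | Formula, x = all records including dose = 0 |
|---|---|---|---|
| Day 1, Day 29 (one omitted) | 28 - 28 = 0 | 28 - 14 = 14 | 29 - 15 - 14 = 0 |
| Day 1, Day 43 (two omitted) | 42 - 42 = 0 | 42 - 14 = 28 | 43 - 29 - 14 = 0 |

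Zero falls in no delay; 14 and 28 fall in 7 or more days. The third reading reconciles formula and words only by setting aside the SAP's restriction to non-zero doses.

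**Step 3. Cycle 1.** Study day of first dose = (date of first dose - date of first dose) + 1 = 1, so the delay is 1 - 1 = 0, whatever the gap from randomization. Measured from randomization, a first dose 3 days later would give 3. The one exception is an Arm B patient given avelumab in error and moved to Arm A for safety (SAP 4.2), whose start day would be Cycle 1 Day 1.

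**Step 4. Feed the delay into the IRR rule.** Take an IRR on Day 1, recorded as 'drug interrupted', with at least 90% of the dose given.

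| Next dose | Words | Formula (non-zero doses) |
|---|---|---|
| Day 15 | 0: IRR removed | 0: IRR removed |
| Day 16-18, inside the window | 1-3: IRR kept | 1-3: IRR kept |
| Day 15 omitted, Day 29 | 0: IRR removed | 14: IRR kept |
| Day 15 omitted, Day 30 | 1: IRR kept | 15: IRR kept |

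Row 2 is the same under every reading. Row 3 is where the readings part, and only the worded definition (or the all-records reading) goes against the stated aim. The Cycle 1 delay appears nowhere in this table, because the rule looks only at the dose after the reaction.

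**The case against.** The best defence is that nobody would code the words. An explicit formula and a two-week example follow them, and the planned gap between consecutive doses on that schedule is naturally 14 days. An omitted Day 15 is then a 14-day delay, a fair description of a 28-day gap, and the IRR in row 3 is correctly kept. This is probably what was intended. It does not remove the conflict in the text, but it supports settling it in favour of the formula.

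The strict test is also defensible: 1-3 days is a named delay category, and keeping more events is the cautious direction. That stands as a design choice. It sits badly, however, with the aim of removing IRRs that only paused an infusion, since a dose inside the visit window need not reflect the reaction at all.

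Several stronger readings are tempting, and the documents do not support them.
- *The rule misclassifies every IRR followed by an omission.* It does so only if the worded (or all-records) reading is programmed and dosing resumes on schedule or early.
- *The Cycle 1 zero distorts the IRR counts.* It never enters them. A late start can also be reported as a protocol deviation (SAP 6.5.2.2).
- *Omitted infusions are invisible.* They lower relative dose intensity (SAP 6.5.3.1). Full doses on Days 1, 29 and 43 give 30 mg/kg over an intended 8 weeks: 30 / (8/4) = 15, and 100 × 15/20 = 75%. What is missing is a count of patients with omissions.
- *Omission is the protocol's only response to toxicity.* Tables 3 to 5 also contain withholding, infusion-rate reduction and permanent discontinuation.
- *A patient count can be given.* Applying the 14.1% Grade 2 IRR rate in Protocol 1.2.2.1 to 668/2 = 334 patients gives about 47. But that rate comes from a pooled Phase 1 cohort, and no document says how often the next dose is late or omitted after an IRR.

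**Conclusion.** The point holds as a defect of definition in two descriptive analyses. For one omitted infusion with dosing resumed on schedule, SAP 6.5.3.3 yields either 0 or 14 days, the best or the worst category. The Cycle 1 delay is zero by construction for patients randomized to and dosed in Arm A. In SAP 6.6.1.3, an IRR recorded as 'drug interrupted' is kept as leading to treatment interruption whenever the next dose is 1 to 3 days late, under every reading. Under the worded definition, an IRR with at least 90% of the dose given and the next infusion omitted would be dropped if dosing then resumed on schedule.

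The arithmetic assumes the two-week schedule and visit windows centred on the nominal day. The number of patients affected cannot be derived from the documents. The effect is confined to the Arm A tables of dose delays and of treatment-emergent events leading to interruption. Overall survival, the alpha split and power are unaffected. It is worth correcting because the correction is cheap, not because it threatens the trial's conclusions.

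**What to change.** These are changes to analysis wording only; no dosing or management rule is touched.

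- **SAP 6.5.3.3, definition.** State that the planned interval between consecutive non-zero doses is 14 days and that x counts non-zero doses only. An omitted infusion then counts as a delay of 7 or more days. This holds at the early edge of the window too: Day 1 to Day 26 gives 26 - 1 - 14 = 11.
- **SAP 6.5.3.3, omissions.** Where dose = 0 records allow, tabulate patients with omitted infusions separately. SAP 6.5.3.1 describes such records only for Day 1 visits, so availability at Day 15 needs checking first.
- **SAP 6.5.3.3, Cycle 1.** Delete the Cycle 1 delay, or measure it from the randomization date.
- **SAP 6.6.1.3.** Keep the 90% dose condition for same-day IRRs. In both bullets, replace no delay with the pooled category of no delay or 1-3 days, which 6.5.3.3 already reports, and require that the next scheduled infusion was not omitted.

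**Cost.** Minor reprogramming. Slightly fewer IRRs will count as leading to interruption, including any that truly pushed the next dose back by 1 to 3 days.
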